4.3.3. Physiotherapy advice leaflet

All participants will receive a physiotherapy advice leaflet providing education and advice about frozen shoulder and pain management, which is especially important during the early pain-predominant stage of frozen shoulder (4). Physiotherapy during the early pain-predominate stage of frozen shoulder is primarily directed at pain relief (e.g. heat, cold and other pain relieving modalities) as forcing the joint to move can make it more painful and is best not pursued. Participants will be advised to take over-the-counter analgesia (e.g. paracetamol with or without codeine, oral or topical nonsteroidal anti-inflammatory drug) as required, in accordance with the BESS guidelines (35). In addition, all of the participants will be provided with advice on modifying activities that exacerbate symptoms and on sleeping positions, drawing on materials used in the GRASP trial (32) and UK FROST trial (12). In addition, the advice leaflet will include a simple set of self-guided physiotherapy exercises, which participants can use once the early pain-predominant stage reduces and to increase shoulder joint mobilisation. Exercises will include passive mobilisation of the shoulder and capsular stretching, drawing on materials used in the UK FroST trial where appropriate (12). Joint mobilisation combined with stretching exercises has been found to be more effective than stretching exercises alone (36, 37). As low health literacy levels are a major consideration when developing materials, plain English and patient representative involvement will be used to optimise material accessibility.

4.3.4. Concomitant care

Participants may seek other forms of treatment during the follow-up period of the trial but will be informed that they should use usual routes (e.g. through GP referral) to do so. Additional treatments (including consultation with primary and secondary care, additional physiotherapy, injection use, or alternative therapies) will be recorded as a treatment outcome as part of the 3 month follow up questionnaire.

4.3.5 Contraindicated medications

Concomitant administration of biologic DMARDs is contraindicated during the treatment period and until 4 months after the last injection. The use of live vaccines must also be avoided until 12 weeks after the last injection.

4.3.6 Post-trial treatment

Participants will transfer to normal care at the end of the trial. There will be no provision of the IMP beyond the trial period.

4.3.7 Compliance with treatment

Adherence to treatment will be defined as receiving an injection within 2 weeks of randomisation. The number of participants receiving a second injection will also be recorded.

4.4. OUTCOMES

4.4.1. Feasibility objectives

The main aim of this feasibility study is to determine whether a future definitive trial would be feasible and to determine the sample size for the definitive trial to assess the effectiveness of adalimumab. We will focus on the main areas of uncertainty relating to the acceptability to be randomised to intra-articular injection of the anti-TNF (adalimumab) and the ability to identify and recruit and treat participants who have pain-predominant early stage frozen shoulder within the current NHS patient pathway for musculoskeletal conditions. In addition, we will collect outcome measures at 3 months, including SPADI and range of shoulder motion.

We have confidence from screening data from the GRASP trial (32) (where frozen shoulder is an exclusion criteria) that there are sufficient potential participants to investigate the feasibility criteria. To determine the feasibility of a definitive randomised controlled trial, the success criteria will be:

- Ability to screen and identify potential participants with pain-predominant stage frozen shoulder.
- Willingness of eligible participants to consent and be randomised to intervention.
- Practicalities of delivering the intervention, including time to first injection and number of participants receiving a second injection.

Data to assess our feasibility objectives will be collected at each site via a trial specific screening log; reasons for ineligibility and / or participants declining to participate in the trial will be recorded where available. The screening log will not contain any patient identifiers and will use screening numbers. Injection details, including time from randomisation to injection delivery, will be monitored based on the information recorded on the trial specific injection treatment logs.

4.4.2. Outcomes

Outcomes (Table 2) will be collected at baseline and at 3-months to assess the feasibility of collecting these in a future definitive trial and to obtain the variability estimates required for estimation of the sample size of the definitive trial. Patient reported outcomes will include shoulder pain and function measured using the SPADI scale (primary outcome for definitive trial) (38, 39); sub-domains of pain (SPADI 5-item pain subscale), function (SPADI 8-item disability subscale) (38, 39); shoulder range of motion (Participant Shoulder Movement Questionnaire); psychological factors (Fear Avoidance Belief Questionnaire) (40); pain self-efficacy questionnaire (41); sleep disturbance (Insomnia Severity Index) (42); patient global impression of change (43); return to desired activities; additional health resource use for index shoulder (e.g. consultation with primary and secondary care, additional physiotherapy, injection use, or alternative therapies).

The choice of outcome measures is based on OMERACT 2016 core outcome set for shoulder disorders (44) and a systematic review of core outcomes used in studies of frozen shoulder (45).

At the 3-month follow up, a blinded outcome assessor will collect an objective measure of shoulder function and performance:

- Participants will undergo measurement of range of motion of the shoulder, including active flexion, extension, abduction internal and external rotation, limitation of which has been shown to be pathognomonic of frozen shoulder in the absence of glenohumeral arthritis (46).

Table 2: Summary of patient outcomes assessed

Outcome	Measurement
Pain and function	Shoulder Pain and Disability Index (SPADI) (38, 39) 13-item total scale
Pain	Shoulder Pain and Disability Index (SPADI) (38, 39) 5-item subscale
Function	Shoulder Pain and Disability Index (SPADI) (38, 39) 8-item subscale
Shoulder range of motion	Participant Shoulder Movement Questionnaire
Psychological factors	Fear Avoidance Belief Questionnaire – physical activity 5-item subscale (40) Pain Self-efficacy questionnaire (short form) (41)
Sleep disturbance	Insomnia Severity Index (42)
Global impression of treatment	Patient-rated Likert scale (43)
Return to desired activities	Patient-reported return to desired activities, including work, social life and sport activities
Health resource use	Patient-reported

Adverse Events	Any Grade 3 or above AEs that have occurred from Consent up until the 3 month Follow up.
----------------	--

See section 7.2. SAFETY REPORTING for safety data collection

4.5. PARTICIPANT TIMELINE

TIMEPOINT (post randomisation unless stated otherwise)	Screening	0-2 weeks	4-5 weeks	3 month follow up
ENROLLMENT:				
Screening log	✓			
Informed consent	✓			
Eligibility confirmed	✓			
Randomisation	✓			
INTERVENTIONS:				
1 st Anti-TNF/placebo injection		✓		
Physiotherapy advice leaflet provision	✓			
2 nd Anti- TNF/placebo injection			✓ ¹	
ASSESSMENTS:				
Serological testing e.g. TB ELISpot, Hepatitis B surface antigen		✓		
Pregnancy testing (if needed)	✓			
Baseline questionnaire	✓			
ROM Assessment	✓			✓
Follow-up questionnaire				✓
Follow-up clinic visit				✓
Qualitative interview (optional)				✓* within 4 weeks of intervention delivery
AE Reporting (grade 3 or above)	✓	✓	✓	✓

1. The second injection must be 2-3 weeks after the 1st injection.

4.6. RECRUITMENT

4.6.1. Recruitment of sites

The feasibility study will be conducted across at least five primary care-based musculoskeletal services and their related physiotherapy services, and as appropriate to local service provision/facilities their local secondary care site in the UK. Participants may also be recruited from directly from NHS secondary-care-based musculoskeletal services, dependant on local service provision at sites. We will utilise our existing network of collaborators from the GRASP trial which recruited from 20 sites in England (32). Sites will be chosen so they reflect a range of settings (urban and rural) and are able to deliver the trial interventions. The local Principal Investigator will be responsible for the conduct of the research at their site. The Principal Investigator will identify the staff responsible for the conduct of the trial and ensure that the trial roles and responsibilities are assigned in writing using the trial delegation log. They will also help with local queries and study promotion. All potential sites will be screened with a site feasibility questionnaire to ensure they have sufficient potential participants and the clinical expertise and capacity to provide the treatments and manage the patients. Participants may also be recruited directly from NHS secondary-care-based musculoskeletal services, dependant on local service provision at sites.

4.6.2. Recruitment of participants

Participants will be recruited from the musculoskeletal services if referred by their GP, physiotherapy service, or self-referred for investigation/treatment of a new episode of shoulder pain. GPs and primary-care-based physiotherapy services within the local area surrounding each study site will be informed about the trial. Posters advertising the Anti-Freeze-F trial will be displayed in local GP surgeries, physiotherapy departments and musculoskeletal clinics to raise awareness of the trial with patients and clinicians. The trial will also have a presence on social media to further raise awareness of the trial amongst the public and professionals as well as being used to provide an update on trial progress. The trial will have a dedicated website hosted by Oxford Clinical Trials Research Unit. We will also contact patient organisations such as the Dupuytren's Society and Diabetes UK which represent patient groups with a high prevalence of frozen shoulder. These methods of recruitment have proved very useful in our trial of anti-TNF injections for people with early stage Dupuytren's disease (47). Participants will be able to claim for reasonable reimbursement for travel to and from their study appointments using the University of Oxford expense form which will be provided in the investigator Site File.

4.6.3. Screening and eligibility assessment

Potential participants will attend their musculoskeletal service clinic appointment in accordance with standard NHS procedures at each site. The treating practitioner will undertake a clinical assessment according to their usual practice. If a patient fulfils the criteria for pain-predominant stage of frozen shoulder, the option to participate in the trial will be discussed and they will be assessed by an appropriately qualified practitioner (i.e. a member of the participant's direct care team) to determine whether they meet the Anti-Freeze-F trial eligibility criteria based on their medical history and where available medical records (as described in Section 4.2) (i.e. no trial specific tests would be undertaken until informed consent is given). Patients will be provided with a copy of the participant information sheet, and asked if they wish to participate in the trial. Patients who meet the eligibility criteria and who would like to participate in the trial will be approached for informed consent and only then will the trial-specific screening tests be undertaken.

4.6.4. Informed consent

Informed consent for participation in the trial will be sought. As part of the process of obtaining informed consent, the exact nature of the study will be explained, what it will involve for the participant including expectations that the participant will be willing and able to attend sessions to receive the study intervention, and any risks involved in taking part. The potential participant will have the opportunity to discuss issues and ask questions. The process of obtaining informed consent may take place during the initial musculoskeletal clinic appointment or may require a second research appointment. This second research appointment may be either face-to-face or virtual depending on local facilities at each site. All participants will be informed that they can decline to participate and can withdraw from the study at any time for any reason without prejudice to future care, and with no obligation to give the reason for withdrawal. We will record anonymised information on the age, ethnicity and sex of those who decline to participate so that we can assess the generalisability of those recruited. Participants may request a follow-up phone call if they require more time to consider the study or wish to speak to their GP or other independent parties before deciding whether they will participate in the study.

A clinical member of the site staff for example A Research Nurse or Clinician Responsible for the patient or another member of the research team who has been trained in Good Clinical Practice (GCP), authorised to do so by the Principal Investigator, will obtain informed consent. A medically qualified doctor will be available during or following the consent process in case of queries relating to their medical care. The process for seeking, confirming and documenting informed consent will be either

paper based (written consent) or digital (eConsent) depending on local facilities at each site. Where consent is taken in person at site, for written consent, the consent form will be signed and dated by the participant and the researcher; a copy of the signed consent form will be given to the participant. The original consent form will be retained at the study site in the Investigator Site File. For consent that is taken digitally within REDCap (handwritten signature using a finger or a stylus or biometric eSignatures), a copy of the participants consent form will be emailed to the participant to an email address provided by them. The eConsent form will be downloaded from SIMS (an Oxford Clinical Trials Research Unit programme that transfers data securely from REDCap so that sites are able to download completed CRFs and consent forms) by the site research team and retained in the Investigator Site File. Electronic tablets will be provided to each site to log onto the REDCap Data Management system to enter the data directly into the trial database.

Where consent is taken remotely, as part of a virtual consultation, eConsent will be used with participants asked to provide a handwritten signature using a finger or a stylus or biometric eSignature on their tablet, mobile phone or other electronic device.

5. METHODS - ASSIGNMENT OF INTERVENTIONS

5.1. ALLOCATION

Consented participants will be randomised to intervention groups (1:1) using a validated web-based centralised randomisation service provided by the Oxford Clinical Trials Research Unit . This will either be undertaken directly by the research team at the site or by contacting the Trial Office over the phone, which will access the system on their behalf, depending on the facilities available at the study sites. If the telephone option is used, site staff will need access to the Screening and Randomisation CRF to provide screening and eligibility details to the Trial Office member of staff so that they can enter these details into the randomisation system and provide site staff with a Trial ID. Randomisation will be computer-generated and stratified by centre, using a variable block size to ensure the participants from each study site have an equal chance of receiving either intervention. Participants will only be randomised following eligibility assessment and after informed consent has been obtained.

5.2. BLINDING

Study participants will be blinded to their treatment allocation. The clinician delivering the treatment injection will not be blinded to the treatment allocation as they will be required to prepare and administer the IMP. They will not be involved with any further trial-specific assessment of the participant. They will be educated on the importance of maintaining the blind of both study participants and the rest of the site staff. All other site staff, except pharmacy staff, will be blinded. The clinician assessed outcomes at the 3 month follow-up clinic visit will be undertaken by a blinded member of the clinical team at site. The trial statistician, Trial Office staff member undertaking checks of dispensed medication, and data entry personnel will not be blinded to the treatment allocation. The remaining members of the trial management team, including the staff conducting the qualitative interviews will be blinded to treatment allocation until after the data analysis is complete.

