6.1.2. Follow-up data collection

Follow up will be conducted via face to face clinic assessment and patient reported questionnaire at 3 months after randomisation. Detail of the outcomes to be assessed, how they will be measured and at which time points are shown in Table 3.

Participants who are unable to attend the face to face appointment will be asked to complete the 3 month follow up questionnaire and return it to the Anti-Freaze-F Trial Office in a prepaid envelope (the ROM participant Questionnaire can only be completed on paper, these will be supplied to the site to send out to participants if needed) or online (web-based version of the questionnaire) as appropriate. The reason why a participant is unable to attend the face to face clinic appointment will be recorded and whether this was due to potential COVID-19 restrictions or due to other reasons. For those who do not respond to the initial 3 month follow up questionnaire a reminder questionnaire will be sent 2 weeks later. Telephone and email follow-up will be used (2 weeks later) to contact those who do not respond to either the initial or reminder questionnaire. For those participants who have requested for digital communication, the ROM will need to be sent to them via the post in paper format. These participants will be send digital reminders if we do not receive the ROM questionnaire back at the trial office. Telephone and email follow-up will also be used to collect a core set of questionnaire items for the Shoulder Pain and Disability Index (SPADI) (primary outcome) if these have not been fully completed on the returned questionnaire.

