6.2. DATA MANAGEMENT

All data will be processed according to the UK General Data Protection Regulations (GDPR) and the Data Protection Act 2018. All documents will be stored safely in confidential conditions. A data management and sharing plan will be produced for the trial and will include reference to confidentiality, access and security arrangements. All trial-specific documents, except for the signed consent form and follow-up contact details, will refer to the participant with a unique study participant number/code and not by name.

Trial data will be collected and managed using REDCap electronic data capture tools hosted at OCTRU, University of Oxford. REDCap (Research Electronic Data Capture) is a secure, web-based application designed to support data capture for research studies, providing 1) an intuitive interface for validated data entry; 2) audit trails for tracking data manipulation and export procedures; 3) automated export procedures for seamless data downloads to common statistical packages; and 4) procedures for importing data from external sources.

Wherever possible, trial data will be entered directly into the trial database by site staff or participants using an electronic tablet provided by the trial, with the questionnaire already opened to complete. Participants and staff should wash their hands or use anti-bacterial gel before handling the tablets to ensure infection control. Data on paper forms or captured during phone calls to participants will be entered into the trial database by suitably trained Trial office staff. Full details will be recorded in the DMP. The participants will be identified by a unique trial specific number in any data extract. Identifiable data will only be accessible by members of the study team with a demonstrated need (managed via access controls within the application) and any additional processing of this will only be for the purposes of communication with the participant (e.g., sending follow-up reminders for online form completion or telephone follow-up).

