6.3. STATISTICAL METHODS

Feasibility outcomes will be reported, including the number of participants approached, those eligible, consenting to randomisation and follow-up, the delivery of intervention (including time to first injection), withdrawal rate, the number receiving a second injection (per group and overall) and data completeness. Baseline characteristics (including possible stratification factors for the definitive trial) will be reported using descriptive statistics, separately per group and overall using the mean and standard deviation (or median and inter-quartile range if non-normally distributed) for continuous variables and the number and percentage of participants in each group for categorical variables. Measures of central location and dispersion of clinical and patient reported outcome measures, including health resource use, at 3 months will be reported and differences between treatments for the intention-to-treat population (i.e. the population of participants as randomised) will be reported with 95% confidence intervals. The standard deviation of the proposed primary outcome for the larger, main trial, SPADI at 3 months, will be used to inform an estimation of the sample size required for the definitive trial. An estimate of treatment effectiveness will be reported together with its 95% confidence interval. This along with change from baseline in range of shoulder motion at 3 months will provide an indication of potential efficacy of the intervention but will not be powered to provide a definitive result, which will only follow the fully powered definitive main trial. Even small increases in range of shoulder motion are important to people with frozen shoulder, where pain and restricted shoulder movement can be very debilitating. As such, we will use a 10-degree improvement in active flexion with any associated improvement in active external rotation of the shoulder to mean a potentially important difference (50). If we observe this difference between groups in our feasibility study with short follow up and a small sample this would indicate potential efficacy, which should then be formally, tested in the full trial. Adverse events and serious adverse events (S/AEs) will be summarised per group and overall in all patients.

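### Data entry personnel are unblinded without a stated reason, and nothing requires the staff who telephone participants or enter 3-month outcomes to be blinded

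*Combined protocol and SAP*

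**What the plan says.** Section 5.2 (Blinding) blinds participants, site staff other than the injecting clinician and pharmacy, and the assessor at the 3-month clinic visit. It then lists the central roles that are not blinded: the trial statistician, the Trial Office member who checks dispensed medication, and data entry personnel. On the last group it says "data entry personnel will not be blinded to the treatment allocation". The section explains why the injecting clinician must know the allocation. It offers no explanation for data entry.

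Section 6.2 (Data management) makes direct electronic entry the preferred route: "Wherever possible, trial data will be entered directly into the trial database by site staff or participants". For the rest, "Data on paper forms or captured during phone calls to participants will be entered into the trial database by suitably trained Trial office staff".

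Section 6.1.2 (Follow-up data collection) shows what can arrive by that second route. For non-responders, "Telephone and email follow-up will be used (2 weeks later) to contact those who do not respond to either the initial or reminder questionnaire". For returned but incomplete questionnaires, "Telephone and email follow-up will also be used to collect a core set of questionnaire items for the Shoulder Pain and Disability Index". The same section says the participant ROM questionnaire can be completed only on paper, and Section 6.2 says the ROM assessment is supplied in paper format.

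Section 4.4.2 names SPADI as the primary outcome of the definitive trial. Section 6.3 says that the standard deviation of "SPADI at 3 months, will be used to inform an estimation of the sample size required for the definitive trial", and also that differences between treatments will be reported with 95% confidence intervals.

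**The concern.** For anything that reaches the database by paper or telephone, Trial Office staff act as data entry personnel, and Section 5.2 says data entry personnel know the allocation. Read together, the sections allow a person who knows a participant's arm to enter that participant's SPADI or ROM answers. They also do not exclude such a person from making the call that obtains them. Prompting for missing items or settling an ambiguous answer while knowing the arm is a recognised way for a subjective outcome to drift in one direction.

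The protocol itself puts weight on this. Its rationale for the saline comparator (Section 3.1.3, Placebo injection) is that blinding matters especially because several outcomes are subjective and patient-reported. The trial summary declares the outcome assessor blind and Section 3.3 calls the design double blind. Someone taking SPADI items by telephone is collecting an outcome, yet nothing guarantees that person is blinded, although Section 5.2 does expressly blind the qualitative interviewers.

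At stake are the reported between-group differences in SPADI and ROM. ROM matters beyond description, because Section 6.5 says a signal of improved range of motion will inform the decision to progress.

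**Working it through.** **Reading the sections together**

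1. Who is unblinded centrally: the statistician, the dispensing checker and data entry personnel (Section 5.2).
2. Who enters paper and telephone data: Trial Office staff (Section 6.2).
3. Which outcomes can come by paper or telephone: SPADI items, whole questionnaires from late responders, and the paper-only participant ROM questionnaire (Section 6.1.2).
4. Who makes the calls: not stated.
5. Any requirement that callers or outcome-entry staff be blinded, or be separate from those handling allocation: none found in Sections 5.2, 6.1.2, 6.2 or 7.4.

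Items 1 to 3 establish the exposure for data entry. Item 4 leaves it open for data collection.

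**The plan's own number**

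Section 5.5 starts from 70 participants and allows 15% attrition: 70 / (1 − 0.15) = 82.4, rounded up to 83, against the stated 84. The figure reproduces to within one participant, and this point does not dispute it. Expected SPADI scores at 3 months: 84 × 0.85 = 71.4.

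**Illustrative size**

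The documents give neither the share of SPADI scores obtained by telephone or paper nor the SPADI standard deviation. Three assumptions follow, none of them from the protocol:

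- share f of scores affected: 5% to 30%, that is 0.05 × 71.4 = 3.6 to 0.30 × 71.4 = 21.4 participants, equal across arms;
- differential error b between arms in those participants: 2 to 10 SPADI points;
- SPADI standard deviation: 15, 20 or 25 points.

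Shift in the between-group mean = f × b:

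| f | b = 2 | b = 5 | b = 10 |
|---|---|---|---|
| 5% | 0.10 | 0.25 | 0.50 |
| 10% | 0.20 | 0.50 | 1.00 |
| 20% | 0.40 | 1.00 | 2.00 |
| 30% | 0.60 | 1.50 | 3.00 |

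Half-width of the unadjusted 95% confidence interval with equal arms = 1.96 × SD × √(4/71.4) = 1.96 × SD × 0.2367:

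- SD 15: 7.0 points
- SD 20: 9.3 points
- SD 25: 11.6 points

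Effect on the SD. If the error is split as +b/2 in one arm and −b/2 in the other, the within-arm variance rises by f(1 − f)(b/2)². In the worst case, f = 0.30, b = 10 and SD 15: √(225 + 0.21 × 25) − 15 = 0.17 points. If the whole 10 points fell in one arm, the pooled variance would rise by half of 0.21 × 100, and √(225 + 10.5) − 15 = 0.35 points. Either is negligible for planning a sample size.

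**The case against.** The best defence is that the exposure is narrow and its main mechanism unproven. Participants are blinded and report SPADI themselves. Direct entry is preferred, so the central route should be the exception. Section 6.2 says who enters telephone data but not who makes the calls, and Section 5.2 keeps the rest of the trial management team blinded, so blinded callers are compatible with the text. Section 6.2 also provides audit trails, access controls for identifiable data and a data management plan that is not among the documents. Copying a blinded participant's written answers leaves little room for bias. The effect estimate is expressly not powered to be definitive, none of the three criteria in Table 4 uses SPADI, and the clinician ROM measurement is made by a blinded assessor.

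Most of this stands as a limit on size. It does not close the gap. The access controls are described for identifiable data, not for allocation. An audit trail records edits but does not prevent prompting. Silence about the caller leaves the most sensitive step unprotected.

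Two stronger readings are tempting and should not be adopted:

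- A reader might see a contradiction between unblinded data entry and blinded site staff who enter data on tablets. Section 5.2 lists data entry personnel among central roles and deals with site staff in a separate sentence. Section 6.2 likewise separates direct entry from Trial Office entry. There is no conflict.
- A reader might infer that no data entry task needs knowledge of the allocation. That is not established. Injection details go on treatment logs and a case report form (Sections 4.3.1 and 4.4.1), paper forms go to the Trial Office (Section 6.2), and Section 7.4 has an unblinded team member review those logs. Handling forms that reveal the allocation is a plausible, though unstated, reason.

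**Conclusion.** The point holds as an avoidable risk of bias created by a stated arrangement. Section 5.2 unblinds data entry personnel without giving a reason, and no section keeps them from outcome calls or outcome entry. The documents do not show that bias will occur or that an unblinded person telephones participants, and neither should be inferred.

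The illustrative shift of 0.1 to 3.0 SPADI points rests wholly on assumed shares and errors. It is below the assumed interval half-width in every case shown. The SPADI standard deviation, which is what this study chiefly needs from SPADI, is essentially unaffected. The relevance is therefore to the reported SPADI and ROM differences, and to any later trial that adopted the same procedure: a bias of this kind does not shrink as the sample grows, while the confidence interval does. Whether the definitive trial would adopt it is unknown, since no protocol for that trial is available.

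The change is worth making because the plan itself rests its choice of comparator on blinding and the remedy costs little.

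**What to change.** In Section 5.2, state that staff who telephone participants or enter 3-month outcome data (SPADI, the ROM forms and the other questionnaires) are blinded to allocation. Limit the entry of forms that reveal allocation, such as injection and dispensing records, to a Trial Office member who is already unblinded, and enforce the split through role-based access in the trial database. Section 6.1.2 should say which role makes the follow-up calls. If there is an operational reason why data entry staff in general must know the allocation, Section 5.2 should give it.

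The cost is a wording change, an access setting and some reallocation of data entry work within the Trial Office. Staffing there is not described, so the change cannot be called free. It is a cheap improvement and leaves the sample size and the analysis unchanged.
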